6.5 Packing density measures

The packing density calculations will be based on total coil length, coil volume, and aneurysm volume. The following equation will be used to calculate the packing density per coiling procedure:

$$\text{Packing density} = \frac{\text{Total Coil Volume}}{\text{Aneurysm Volume}} \times 100$$

The coil volume calculation assumes a cylindrical shape of the coil:

$$\text{Coil Volume} = \frac{\pi \times Dc^2 \times L}{4}$$

Dc: Coil outer diameter

L: Coil length

The aneurysm volume will be calculated using the following equation:

$$\text{Aneurysm Volume} = 4/3 \pi (a/2)(b/2)(c/2)$$

a, b, and c are the aneurysmal height, length and width in millimeters.

In order to keep measurements as uniform as possible, the Imaging Core Lab will provide the aneurysm volume and the treating physician will provide the total coil volume as the Imaging Core Lab will be blinded to the type of coils used.

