3.2 First Generation of the HydroCoil Embolic System: HydroCoil®

The first generation of the HydroCoil Embolic System is constructed using a core platinum coil surrounded by a sleeve of expandable hydrogel and an outer wire with gaps which allow expansion to occur. As such, the Hydrogel device is relatively stiff because of its dehydrated state, especially when compared to soft, platinum coils. The Hydrogel undergoes substantial swelling over time, markedly increasing its outer diameter and surface area over approximately 20 minutes. The increase in volume of the coil varies among the different HydroCoils. The HydroCoil 10 swells up to 0.022”, 5 times the volume of a platinum 10 coil; the HydroCoil 14 and HydroCoil 18 swell to 3 and 6 times the volume of Platinum 18 coils, respectively. The HydroCoil 14 and 18 coils swell up to 0.027” and 0.034”, respectively. Although substantial swelling is advantageous for aneurysm filling volume, there are limits associated with deployment time and size of the coils. Difficulty in deployment may lead to the need for multiple repositionings and potential untoward early swelling of the device which limits delivery through certain microcatheter systems. The HydroCoil is generally used as filling coils.

3.3 Second Generation of the HydroCoil Embolic System: HydroSoft®, HydroFrame®, HydroFill® and Future Hydrogel Products

In an attempt to offer a hydrogel coil as a soft finishing coil to allow ease in placing gel coils at the neck of the aneurysm, MicroVention developed the HydroSoft® line of embolic coils. These coils which are constructed with a filament of expandable hydrogel within the platinum coil are essentially as soft as platinum coils based on benchtop experiments and thus have handling properties similar to traditional platinum coils. Furthermore, since the hydrogel does not expand excessively, repositioning time is markedly prolonged to 30 minutes per the Instructions for Use (IFU). When fully hydrated, the HydroSoft swells up to approximately

0.013" to fill the gaps between the spirals of the platinum coil.^{7,9} The HydroSoft coils are primarily used as finishing or filling coils.

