The next coil introduced by MicroVention, Inc., was HydroFrame®, a framing coil with hydrogel on the inside of the coil that is available in both 10 and 18 systems. MicroVention then developed HydroFill® which is used primarily as a filling coil, has a longer working time than HydroCoil (10 minutes in a .0165 microcatheter or 30 minutes in a .021 microcatheter), and swells to .018". The HydroFrame®, HydroSoft® and HydroFill® do *not* require steaming or prepping of the coil.

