4.3 Secondary Outcomes

- Packing density as measured by the volumetric filling of the aneurysm
- Rate of initial complete occlusion
- Procedure and/or device-related morbidity and mortality
- Clinical outcome at 18 to 24 months as assessed using the modified Rankin Scale
- Re-treatment rates
- Hemorrhage from target aneurysm during follow-up
- Aneurysm occlusion stability
- Major versus minor recurrence

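### Packing density depends on the square of a coil diameter whose dry or hydrated state is not fixed, and each treating physician supplies the coil volume, so sites can use different conventions within the hydrogel arm

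*Combined protocol and SAP*

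**What the plan says.** Section 6.5 defines packing density as total coil volume divided by aneurysm volume, times 100. It states that "The coil volume calculation assumes a cylindrical shape of the coil", which gives π × Dc² × L / 4. The only explanation of Dc is "Dc: Coil outer diameter". The two parts of the ratio come from different people: "the Imaging Core Lab will provide the aneurysm volume and the treating physician will provide the total coil volume". The reason given is that the core lab is blinded to coil type. The section contains no table of diameters and does not refer back to the device description.

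That description, in section 3.3, shows that the trial's hydrogel coils change size. It says that "the HydroSoft swells up to approximately" 0.013 inch, and that HydroFill has a longer working time than the first-generation coil "and swells to .018" inch. It gives no dry diameter for either. HydroFrame is described only as coming in 10 and 18 systems, with no diameter in either state. Future hydrogel products are also allowed in the arm.

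Section 4.3 lists as a secondary outcome "Packing density as measured by the volumetric filling of the aneurysm", and section 4.1 makes higher packing density part of the hypothesis. Section 9.2.2 compares the arms by means or medians and by linear regression adjusted for site and other covariates. Section 9.2.1 also lists packing density among the covariates for the adjusted logistic model of recurrence.

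**The concern.** A platinum coil has one outer diameter. A hydrogel coil has two, and the formula squares whichever is entered. The missing definition therefore acts on one arm only and moves the between-arm difference directly.

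If one analyst computed every volume, a single convention would at least be applied throughout. Under section 6.5, however, the finished volume comes from the treating physician at each of up to 50 centers (section 5.2), and that physician has just implanted the coils and knows the arm. Nothing in the plan stops one site from using the packaged diameter and another the swollen one.

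Adjusting for site does not remove this. A site term shifts both arms at a site equally, whereas the convention changes only the hydrogel patients there. It is a site-by-arm difference, and it passes into the estimated coil effect. The same inconsistent values then enter the adjusted recurrence model as a covariate.

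**Working it through.** The plan states no expected value, standard deviation or power for packing density, so there is no figure of its own to reproduce. The check asks how far the result moves with the choice of diameter.

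**Formula.** At fixed length and aneurysm volume, packing density (hydrated) / packing density (dry) = (hydrated Dc / dry Dc)².

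**Inputs from section 3.3.** Hydrated HydroFill 0.018 inch; hydrated HydroSoft about 0.013 inch.

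**Assumed dry sizes, with their basis.**
- Low value: 0.0098 inch, the platinum 10 diameter implied by section 3.2. There, a first-generation HydroCoil 10 swells to 0.022 inch and has 5 times the volume of a platinum 10 coil, so 0.022/√5 = 0.0098. This stands in for a second-generation dry diameter; it is not a stated one.
- High value for HydroFill: 0.0165 inch. Section 3.3 says the coil can be delivered through a .0165 microcatheter; I take that figure as the inner diameter.
- High value for HydroSoft: 0.012 inch for the stated range, approaching 0.013 inch in the limit.

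**HydroFill, hydrated over dry.**
- dry 0.0098: (0.018/0.0098)² ≈ 3.3
- dry 0.010: 3.24
- dry 0.012: 2.25
- dry 0.014: 1.65
- dry 0.0165: 1.19

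**HydroSoft, hydrated over dry.**
- dry 0.0098: (0.013/0.0098)² ≈ 1.7
- dry 0.010: 1.69
- dry 0.012: 1.17
- dry 0.013: 1.00

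**Mixtures by length.**
- Half HydroFill, half HydroSoft, both 0.010 dry: (0.5 × 0.018² + 0.5 × 0.013²) / 0.010² = 2.46.
- 90% HydroFill with the permitted 10% platinum, all 0.010 dry: (0.9 × 0.018² + 0.1 × 0.010²) / 0.010² = 3.02.

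**What a threefold change would need.** HydroFill: 0.018/√3 = 0.0104 inch dry. HydroSoft: 0.013/√3 = 0.0075 inch dry. Threefold therefore requires packing almost wholly with HydroFill at a dry size near 0.010 inch.

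**On the packing-density scale.** Assume a 6 mm spherical aneurysm (113 mm³) and 60 cm of coil. The formula gives 26% at 0.0098 inch, 45% at 0.013 inch and 87% at 0.018 inch, for the same coil length.

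**Mixed conventions.** If a share q of hydrogel patients is entered with the hydrated diameter and the rest dry, and true packing is the same in both groups, the arm mean is 1 + q(r − 1) times the all-dry mean. With r = 2.46 and, for illustration, q = 0.5, this is 1 + 0.5 × 1.46 = 1.73. The result then depends on how many sites chose which diameter, and the spread within the arm is widened as well.

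**For scale.** Section 3.5 cites mean packing densities of 73% and 32% for first-generation HydroCoil and platinum, a ratio of 73/32 = 2.3. Under the even-mix assumption, the convention alone can move the hydrogel figure by a factor of that order.

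**The case against.** Context favors the hydrated reading. The endpoint is described as volumetric filling, and the only second-generation coil diameters printed are swollen ones. This narrows the ambiguity without removing it: section 6.5 does not cite those figures, and for HydroFrame there is none to cite.

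The HydroSoft effect may be small. Its gel lies inside the platinum winding, is said not to expand excessively, and fills the spaces between the turns. A dry outer diameter close to 0.013 inch fits that description, with a ratio near 1. This stands, and it is why the HydroSoft range has to be left open at the lower end.

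Mixing between sites is possible but not established. The case report forms are not part of these documents. The 10% platinum rule is based on length, so length by coil type must be known, and a form might compute volume from it. But the protocol text says that "the treating physician will provide the total coil volume", and even a central calculation would need a stated diameter.

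Three stronger readings are tempting and not supported.
- **A threefold distortion of the arm as a whole.** No second-generation dry diameter is given, and the arm uses framing, filling and finishing coils. Threefold is an assumption-based ceiling for near-exclusive HydroFill use.
- **Hydrated HydroFill having 3.3 times the volume of a platinum 10 coil as a measure of error.** A swollen coil does occupy more space; that is how the device works. Any bare platinum coil is also allowed. The same back-calculation for platinum 18 gives 0.027/√3 = 0.0156 inch or 0.034/√6 = 0.0139 inch. These disagree, so the method is rough. Against them, hydrated HydroFill has 1.3 to 1.7 times the volume and HydroSoft 0.7 to 0.9 times.
- **A reversed direction of the arm difference.** With a dry hydrogel diameter of 0.0098 inch or more, hydrogel volume per unit length is at least that of a platinum 10 coil under either convention. A reversal would need shorter hydrogel lengths or thicker platinum coils, and the documents give no implanted lengths or mix of coil sizes from which to judge that.

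**Conclusion.** The point holds as a defect of definition and of who does the calculation. Section 6.5 squares a diameter that is not tied to a dry or hydrated state, and it leaves the resulting volume to unblinded physicians at many sites. The packing-density comparison and the packing-density covariate in the adjusted recurrence model are both exposed. The unadjusted chi-square test of recurrence is not.

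The size rests on assumed dry diameters: a ratio of about 1.2 to 3.3 for HydroFill (dry 0.0165 down to 0.0098 inch), about 1.2 to 1.7 for HydroSoft (dry 0.012 down to 0.0098 inch, and smaller nearer 0.013 inch), and about 2.5 for an even mix at about 0.010 inch. No range can be given for HydroFrame. The documents permit inconsistent conventions; they do not show that any site used them. The correction should be made, but it does not put the unadjusted primary comparison in doubt.

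**What to change.** 1. Replace the physician-supplied volume with site entry of the product and length of every implanted coil.
2. Compute coil volume centrally from one fixed table of diameters covering all hydrogel and platinum products used, with dry and hydrated values for the hydrogel coils, including HydroFrame.
3. State in section 6.5 which diameter is used for the main analysis, and fix this before anyone analyzes packing density by arm. Hydrated fits the endpoint's description as volumetric filling.
4. Report the other convention as a pre-specified sensitivity analysis, both for the arm comparison and wherever packing density enters the adjusted recurrence model.

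The cost is a paragraph of protocol text, the table and a short program. The core lab stays blinded to coil type, because it still supplies only aneurysm volume. The table must be kept up to date for every bare platinum coil used and for future hydrogel products, and two packing-density figures are reported instead of one.

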6.6 Treatment protocol

6.6.1 Coiling procedure

Coiling will be performed according to the standards of each institution. The choice of catheters and guide-wires will not be dictated. The investigator will also have the choice to use assist devices (balloon and/or stents). The use of assist devices will be recorded on the Procedure eCRF. No flow diverter stents are to be utilized in this study. Coiling will be done in a one-step procedure. Every attempt should be made to treat with as much of the randomized coil type as possible to achieve optimal occlusion. Use of any bioactive or non-HES 2nd generation coils (e.g. Matrix, EV3 or Cerecyte) and/or use of liquid embolic materials is not allowed. Use of such devices will be considered a protocol deviation but the subject will continue to be followed according to HEAT protocol.

The use of Antiplatelet therapy is left to the discretion of the treating physician. Antiplatelet therapy type and dosing should be recorded on the eCRF. Timing of anticoagulation and ACT during the procedure should be documented on the eCRF.

For the Platinum group, any type of FDA or HPB approved or cleared (as applicable) bare platinum coils can be used. For the Hydrogel group, the investigator will use any type of FDA or HPB approved or cleared (as applicable) second generation HydroCoil Embolic System product (which includes HydroSoft, HydroFrame, HydroFill and future FDA or HPB approved hydrogel products). For subjects randomized to the Platinum arm, treatment should involve exclusive use of bare platinum coils. For subjects randomized to the Hydrogel arm, treatment should involve exclusive use of HES products with up to 10% of total coil length using bare platinum allowed.

After the procedure, digital copies of the pre and post-coiling angiograms with AP and lateral working projections will be sent to the Imaging Core Lab for independent evaluation and analysis. A copy will also be sent to the Sponsor, Northwestern University. The images will be de-identified and the CD/DVD will be labeled with the subject's assigned study identification number, imaging type, and date of imaging.

6.7 Post-procedure follow-up: Day 1 post-coiling

On day 1 post-coiling, clinical and neurological assessment of the subject is performed and documented on the eCRFs. This visit involves a mRS assessment for all subjects and NIHSS and Hunt & Hess scale assessments for subjects presenting with a ruptured aneurysm.

6.8 Immediate follow-up visit: Between 3 to 28 Days post-coiling

The immediate post-coiling follow-up will consist of a clinical assessment and specifically a neurological exam. This visit involves a mRS assessment for all subjects and NIHSS and Hunt & Hess scale assessments for subjects presenting with a ruptured aneurysm. The investigator or an authorized member of the research team will assess for any new or unresolved adverse events. The need for cerebral imaging will be assessed and performed according to the standard of care at each institution to evaluate aneurysm occlusion and to study the early recanalization rate. If the length of hospitalization post-procedure equals or exceeds 3 days, then the 3 to 28 day follow-up will also be considered as the discharge follow-up and it will be marked as such on the eCRF. If a 3-28 day visit is not standard of care at a site, the mRS score and review of adverse events can be obtained via phone.

6.9 Early follow-up Visit: Between 3 months to 12 months post-coiling

Clinical and neurological assessments will be performed. The neurological examination will include the mRS. The investigator or an authorized member of the research team will assess for any new or unresolved adverse events. A digital subtraction cerebral angiogram will be performed. MRA can be performed instead of or in addition to the angiogram if considered standard of care at the institution. Quality of life will be assessed with the SF-36 questionnaire. For subjects enrolled with ruptured aneurysms, an NIHSS score will also be obtained.

6.10 Final follow-up Visit: Between 18 to 24 months post-coiling

Clinical and neurological assessments will be performed. The neurological examination will include the mRS. The investigator or an authorized member of the research team will assess for any new or unresolved adverse events. A digital subtraction cerebral angiogram will be performed. MRA can be performed instead of or in addition to the angiogram if considered standard of care at the institution. Quality of life will be assessed with the SF-36 questionnaire. For subjects enrolled with ruptured aneurysms, an NIHSS score will also be obtained.

6.11 Unscheduled Follow-up Visit

Should an unscheduled follow-up visit occur, the reason for the visit should be clearly marked in the eCRF. In the event there is a change in the clinical neurological status due to an adverse event/serious adverse event, the mRS score should be assessed and entered in the eCRF. If the subject presents with a hemorrhage, the NIHSS and Hunt and Hess scores should be assessed and entered in the eCRF. The investigator or an authorized member of the research team should assess and report any unresolved or new adverse events. If imaging is ordered to assess occlusion or recurrence of the aneurysm, the Imaging eCRF must be completed and the imaging CD should be sent to the Imaging Core Lab and the Sponsor, Northwestern University. If imaging is performed for purposes other than to assess occlusion or recurrence, the Imaging eCRF does not need to be completed and no CD is required for submission.

6.11.1 Re-treated Subjects

For subjects who are retreated, please complete the Unscheduled follow-up visit. If a subject is retreated by coiling or stent-coil, sites will need to send the images to both the **IMAGING CORE LAB** and **Sponsor**.

For subjects who were retreated prior to their 18-24 Month follow-up visit, please follow the above depending on how the subject was treated.

6.12 Schedule of Assessments

A summary of the study related assessments as outlined above is described in Table 4.

6.13 Study Completion

Once a subject completes all study follow-up visits which include the 18 to 24 month visit, the Final Follow-Up eCRF must be completed. During the course of the study, it is possible that subjects will be

withdrawn from the study prior to completing the final 18 to 24 months visit. Factors leading to Subject withdrawal may include, but are not limited to the following:

- **Subject Withdrawal** - A Subject may voluntarily withdraw from the study at any time for any reason, whether disclosed or undisclosed, without affecting their future medical treatment or benefits. In addition, if a patient refuses follow-up examinations and evaluations the investigator may remove her/him from the study after appropriate notice.
- **Subject Lost to Follow-Up** – If the subject does not show up to the planned follow-up visits, attempts should be made to contact her/him. If after at least three (3) attempts the subject remains unreachable, she/he may be withdrawn from the study. The research team must document at least three contact attempts before declaring a subject as lost to follow-up.
- **Subject Death** - When a Subject dies, the ADVERSE EVENT and STUDY EXIT eCRFs must be completed immediately (within 24 hours of the event). If available, documents such as the death summary, the autopsy report and a copy of the death certificate shall be provided to the principal investigator of the site and the Sponsor, Northwestern University, and the funder, MicroVenton. Personal identifiers should be removed from any documentation provided. The site's IRB shall also be notified promptly.

If a subject was withdrawn for any of the above mentioned reasons, the Study Exit eCRF form must be completed.

7 Management of Adverse Events

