5.3.1 Informed Consent

Prior to Subject participation in this study, the study team must obtain written IRB approval for the protocol and the Informed Consent Form (ICF). Once the patient's potential eligibility has been determined, the investigator or an IRB approved member of the research team will discuss the study and ask the patient if they are interested in participating in the study. The study will be explained to the patient in lay terms or at the level of patient understanding. The differences in coiling types will be explained in full detail. The approved ICF must be signed prior to performing study related assessments. The subject will be given a copy of the signed and dated ICF. The informed consent process must be documented and placed in the subject binder. Failure to obtain a signed ICF prior to the procedure constitutes a protocol deviation. It must be clear to subjects that they may withdraw from the study at any time and for any reason without penalty. It will be made clear to study participants that withdrawal from the study will not adversely affect their medical treatment and they will continue to receive therapy as indicated by their physician. Data from subjects obtained prior to withdrawal may be used for statistical analysis but no further data will be obtained.

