6.1 Screening and Consent

Eligibility will be assessed once the neurovascular team makes a decision on endovascular treatment of an aneurysm. A local site log of all eligible patients will be kept and a copy returned to the coordinating site (Northwestern University) when requested by the study monitor.

If a patient fulfills the inclusion and exclusion criteria, an authorized member of the research team will discuss the trial and provide the patient or his/her LAR with the informed consent form. The patient or LAR will be provided adequate time to consider participation in the trial and the research team will answer all questions regarding the trial. A copy of the consent will be retained in the patient's medical record, one will be given to the patient, and the original will be retained by the local site.

All patients who meet the eligibility criteria and give written informed consent are eligible for enrollment into the study which occurs at the time of randomization

Screen failures are defined as a subject consented and screened for enrollment, but not ultimately enrolled on the day of randomization; provided that the failure to enroll was attributable to the subject's failure to meet the inclusion or exclusion criteria listed in the protocol.

Screen failures and subjects who electively withdraw from the study will be dropped from any further follow-up and statistical analysis of this study. The original ICF and any data collected up until the date of withdrawal will be maintained in the clinical site's study files and their number will not be used again in the study.

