8.2 IRB Approval

The Investigator or the study coordinator is responsible for submitting the study protocol and any changes issued by the Sponsor during the course of the study for IRB approval prior to any Subject enrollment and amendments taking effect as well as obtain renewals at periods determined by the IRB for the duration of the study.

9 Statistical Methods

Primary analysis of primary and secondary outcomes will be based on the intent-to-treat (ITT) principle. Secondary analyses will examine differences based on per protocol principles, as well as a detailed analysis of missing data, should there be any (see below).

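### Section 6.13 allows subjects who refuse follow-up or cannot be reached to be taken out of the study without withdrawing consent, so 18-24 month clinical outcomes that need no study scan can be lost

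*Combined protocol and SAP*

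**What the plan says.** Section 6.13 lists ways in which a subject may leave before the final visit. Under voluntary withdrawal it adds that "if a patient refuses follow-up examinations and evaluations the investigator may remove her/him from the study after appropriate notice". Under loss to follow-up it says "If the subject does not show up to the planned follow-up visits, attempts should be made to contact her/him", and then "If after at least three (3) attempts the subject remains unreachable, she/he may be withdrawn from the study". The attempts must be documented, and a Study Exit form follows in every case.

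Two other sections say what happens to the data. Section 5.3.1 states: "Data from subjects obtained prior to withdrawal may be used for statistical analysis but no further data will be obtained". Section 6.1 states that "subjects who electively withdraw from the study will be dropped from any further follow-up and statistical analysis of this study".

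The outcomes at issue are in the Synopsis and Section 4.3. They include "Clinical outcome at 18 to 24 months as assessed using the modified Rankin Scale", together with mortality, retreatment and bleeding from the treated aneurysm. Section 9 opens with: "Primary analysis of primary and secondary outcomes will be based on the intent-to-treat (ITT) principle".

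For the 3-28 day visit, Section 6.8 allows that "the mRS score and review of adverse events can be obtained via phone" at sites where that visit is not routine. Sections 6.9 and 6.10 give no such option for the early and final visits.

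**The concern.** The protocol does not separate missing an assessment from leaving the study. A subject who declines some follow-up, or who is away when the early visit falls due, can be exited while still consenting to be followed. Nothing provides for clinical-only follow-up, a later call, a check of the treating record or a check of vital status.

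The outcomes lost this way are ones a phone call or a hospital record could often supply. Exit at the early visit also forgoes the final scan, which counts towards the primary endpoint because that endpoint covers progression at any time in follow-up.

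The treating side knows the coil type: under Section 6.5 the treating physician supplies the coil volume, while the Imaging Core Lab is blinded to the type of coil. If willingness to attend, or the decision to remove, is related to how the subject is doing, the remaining subjects no longer represent the randomized groups.

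**Working it through.** **1. Is withdrawn consent required?** No. Under Section 6.13 the refusal rule is triggered by refusal plus the investigator's decision and notice. The unreachable rule is triggered by non-attendance plus at least three documented attempts.

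**2. When can the unreachable rule apply?** The text refers to planned follow-up visits without distinguishing them, so the 3-12 month visit is included. The final window opens at month 18. Counted from the end of the early window this is 18 − 12 = 6 months later; from its start, 18 − 3 = 15 months later. Nothing requires the site to wait or to call again.

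**3. What happens to the data?** Three statements need to be set side by side:
- Section 5.3.1: earlier data may be used; nothing more is collected.
- Section 6.1: elective withdrawals leave both follow-up and analysis.
- Section 9: the primary analysis of all primary and secondary outcomes follows ITT.

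The first two disagree on whether data obtained before withdrawal are analysed, and the second conflicts with the third. Section 6.1 names only elective withdrawals. Section 6.13 places removal for refusal under the subject-withdrawal item, so it is unclear which treatment such a subject receives.

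**4. Does the protocol retain subjects elsewhere?** Yes. Section 6.3 keeps crossovers, staged coiling and flow-diverter cases in protocol follow-up, and follows subjects switched to surgery or left untreated according to standard of care.

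**5. Power.** Inputs from Section 9.1 and Table 5: 300 per arm, two-sided 5% level, chi-square test; retreatment 17.4% vs 9.6%; recurrence 33.0% vs 22.8%. With p̄ the mean of the two rates, q = 1 − p and n per arm:

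Power = Φ{ [ |p1 − p2|√n − 1.960√(2p̄q̄) ] / √(p1q1 + p2q2) }

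*Retreatment:* p̄ = 0.135, √(2p̄q̄) = 0.4833, √(p1q1 + p2q2) = 0.4801.
- n = 300: (0.078 × 17.321 − 0.9472)/0.4801 = 0.841, power 80.0%
- n = 270: (0.078 × 16.432 − 0.9472)/0.4801 = 0.697, power 75.7%
- n = 240: (0.078 × 15.492 − 0.9472)/0.4801 = 0.544, power 70.7%

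*Recurrence:* p̄ = 0.279, √(2p̄q̄) = 0.6343, √(p1q1 + p2q2) = 0.6302.
- n = 300: (0.102 × 17.321 − 1.2432)/0.6302 = 0.831, power 79.7%
- n = 270: 0.687, power 75.4%
- n = 240: 0.535, power 70.4%

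The plan's 80% at N = 600 is reproduced, and only with all 600 subjects analysed. The 10% and 20% losses are assumptions, and the calculation treats the loss as unrelated to outcome. It shows sensitivity to loss from any cause; it does not predict what Section 6.13 would cause.

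**The case against.** The strongest reply is that the clauses are permissive and guarded. Removal needs notice, or three documented attempts, and a sensible investigator need not use it. The refusal clause joins examinations with evaluations, and Sections 6.9 and 6.10 use examination for the neurological assessment and list the angiogram separately. On that reading the clause is aimed at someone refusing clinical assessment altogether. Eligibility also screens for willingness and ability to attend (inclusion 6, exclusions 12 and 14), and MRA may replace the angiogram where that is standard of care. Sections 9.2.1 and 9.2.2 foresee examination of dropout patterns, possible imputation and mixed models on available data.

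Much of this stands. A reader might infer that the protocol discards these outcomes by rule; it does not, because removal is a choice. A reader might infer that removal will differ between arms; the documents show an opportunity for that and no evidence of it. A reader might turn Table 2's 51% to 90% followed up into a count of subjects lost. Those are earlier series of mixed design, and the table does not separate refusal from other loss or say who was still reachable. A reader might also expect phone calls to restore the recurrence analysis; they cannot, because recurrence needs imaging. Retreatment is only partly free of the scan: an unscanned subject may be untreated because recanalization was never seen.

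The reply does not remove the point. The wording does not limit the refusal clause to people who refuse everything, and the ambiguity is itself a reason to clarify. Models for missing data rest on assumptions about why data are missing, and discretionary removal by someone who knows the arm could breach them.

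**Conclusion.** The concern holds as a permitted and avoidable loss. Section 6.13, read with Sections 5.3.1 and 6.1, allows the 18-24 month mRS, mortality, hemorrhage and recorded retreatment to be lost for subjects who have not withdrawn consent, and this is at odds with the declared ITT analysis. The number affected cannot be derived from the documents. The principal issue is possible informative loss; its direction and size are unknown. The power effect is secondary: about 4 percentage points for an assumed 10% loss and about 9 for 20%, for either outcome. Clinical follow-up of removed subjects could recover the retreatment part only. For recurrence, the gain is confined to early-visit absentees who return for the final scan. The change is cheap enough to be worth making even if few subjects would be affected.

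**What to change.** Amend Section 6.13 to say:
- A refused or missed visit, angiogram or MRA is recorded as a missed assessment and is not withdrawal. Delete the investigator's option to remove a subject for refusal.
- Where the subject still consents to contact, mRS, adverse events, retreatment, target-aneurysm hemorrhage and vital status are obtained at later windows by phone or from the treating record.
- A subject missed at 3-12 months is contacted again for the 18-24 month visit and scan.
- Loss to follow-up is declared only after three documented attempts within the 18-24 month window.
- Only the subject's own withdrawal of consent, or death, ends data collection.

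Reconcile Sections 5.3.1 and 6.1 with the ITT statement in Section 9, so that data collected before withdrawal are analysed in the randomized arm.

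The cost is protocol wording, an eCRF entry for a missed assessment and some extra calls. Section 8.2 requires IRB approval before an amendment takes effect, and Section 5.2 foresees up to 50 centers. Use of treating records may need a matching change to the consent form.
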